10.9. Appendix 9: COVID-19 Pandemic and Clinical Trial Continuity

The COVID-19 pandemic may impact the conduct of clinical studies. Significant logistical challenges may arise from quarantines, variable restrictions on site resource and operations, site closures, travel limitations and the inability of an individual participant to attend clinic visit, interruptions to the supply chain for the investigational product, or other considerations if site personnel or study participants become infected with COVID-19. These challenges may lead to difficulties in meeting protocol-specified procedures, including dispensation of the investigational product to the participant or adhering to protocol-mandated visits and laboratory/diagnostic testing.

Based on these challenges, it may be necessary to adopt additional measures and procedures to protect participant safety, and to ensure that there are no gaps in study treatment for participants enrolled in this clinical study.

In order to maintain the scientific integrity of the study, and adhere to updated guidance from regulators, procedures have also been put into place to ensure that the actions taken to mitigate against any impact of COVID-19 are well documented in the trial database.

This appendix outlines the measures which are approved for implementation within this clinical trial, to protect patient safety, welfare and rights, and to ensure data integrity and the integrity of the clinical trial, as a result of COVID-19 only. These measures may be implemented in accordance with any requirements and expectations set out by local Independent Review Boards/Independent Ethics Committees and National Competent Authorities, as necessary.

This appendix **does not** apply for participant management issues that are unrelated to a specific, and documented, impact from COVID-19.

10.9.1. Changes to Study Visits and Study Procedures

- There may be cases where the current principal investigator (PI) of a site is indisposed for a period and may need to delegate parts of his/her duties temporarily, e.g. to a sub-investigator. Any such changes should be documented in the site's source records. Any permanent changes in PI should be communicated to the sponsor.
- There may also be circumstances where immediate actions are required by the sponsor and/or investigator, outside of what is contemplated in the protocol, in order to protect a study participant from immediate hazard. Any such measures will be carefully documented and conducted in accordance with the National Competent Authority (NCA)/IRB/IEC regulations.

10.9.2. COVID-19 Experimental Agents

If any treatments for COVID-19 are planned for a study participant, please consult with the study medical monitor to ensure that relevant drug interactions are considered and to ensure that continued study participation remains appropriate.

The protocol does not allow for concurrent enrolment in other interventional studies, though, there may be exceptions in this pandemic. If a participant is being considered for enrolment into clinical studies for COVID-19 treatment or vaccinations, please reach out to the Medical Monitor who will discuss with the study team (to include Safety Review Team and input from the PK Scientist/Clinical Pharmacologist) who will consider relevant drug interactions and to ensure that continued study participation remains appropriate.

10.9.3. COVID-19 Specific Data Capture

10.9.3.1. Capturing COVID-19 Specific Protocol Deviations

Please refer to the SRM for specific details on capturing protocol deviations as a result of COVID-19.

10.9.3.2. Capturing COVID-19 Specific AEs and SAEs

ViiV Healthcare are monitoring the evolving situation with respect to COVID-19 carefully and the impact this may have on ongoing or planned clinical trials. It is important for the study team to describe COVID-19 related adverse events/serious adverse events and their impact on study data and outcomes. Standardization of case definitions will facilitate future data analysis.

Please use the following guidance:

1. AEs should continue to be evaluated as to whether they meet SAE criteria as defined in the protocol, and if so, submitted according to established SAE reporting requirements. SAEs and AEs should be submitted following usual study procedures and timelines.
2. Investigators should use the WHO definition to classify COVID-19 cases. The definition below, released March 20, 2020, represents a time point for standardized collection. We recognize definitions are likely to continue to evolve; the most recent definitions should be consulted for each case (WHO). When reporting both serious and non-serious adverse events (related to COVID-19 infection), investigators should use the following Verbatim terms:
 - a) Suspected COVID-19 infection; or
 - b) Probable COVID-19 infection; or
 - c) Confirmed COVID-19 infection

Sites should contact the study Medical Monitor for questions related to definitions and reporting, and decisions around impact to study drug continuation.

3. A new COVID-19 infection Case Report Form will be included in the eCRF to collect additional details about the reported COVID-19 AE or SAE data. It is important that the correct information is collected from each participant reporting a COVID-19 AE or SAE. Therefore, please use the CRF templates to help you collect this information for all COVID-19 related AEs/SAEs.

10.9.3.2.1. WHO Case Definition (March 20, 2020 Version):**Suspected case:**

- A. A patient with acute respiratory illness (fever and at least one sign/symptom of respiratory disease, e.g., cough, shortness of breath), AND a history of travel to or residence in a location reporting community transmission of COVID-19 disease during the 14 days prior to symptom onset;

OR

- B. A patient with any acute respiratory illness AND having been in contact (see definition of “contact” below) with a confirmed or probable COVID-19 case (see definition of contact) in the last 14 days prior to symptom onset;

OR

- C. A patient with severe acute respiratory illness (fever and at least one sign/symptom of respiratory disease, e.g., cough, shortness of breath; AND requiring hospitalization) AND in the absence of an alternative diagnosis that fully explains the clinical presentation.

Probable case:

- A. A suspect case for whom testing for the COVID-19 virus is inconclusive (Inconclusive being the result of the test reported by the laboratory).

OR

- B. A suspect case for whom testing could not be performed for any reason.

Confirmed case:

A person with laboratory confirmation of COVID-19 infection, irrespective of clinical signs and symptoms.

COVID-19 Contact:

A contact is a person who experienced any one of the following exposures during the 2 days before and the 14 days after the onset of symptoms of a probable or confirmed case:

1. Face-to-face contact with a probable or confirmed case within 1 meter and for more than 15 minutes;
2. Direct physical contact with a probable or confirmed case;
3. Direct care for a patient with probable or confirmed COVID-19 disease without using proper personal protective equipment; OR
4. Other situations as indicated by local risk assessments.

Note: for confirmed asymptomatic cases, the period of contact is measured as the 2 days before through the 14 days after the date on which the sample was taken which led to confirmation.

10.10. Protocol Amendment History

The Protocol Amendment Summary of Changes Table for the current amendment is located directly before the Table of Contents (TOC).

1. INTRODUCTION

The purpose of this SAP is to describe the planned analyses to be included in the Clinical Study Report for Study 213051. Details of the final analyses are provided.

Descriptive study population analyses such as summary of demography and baseline characteristics and additional detail with regards to data handling conventions and the specification of data displays will be provided in the Output and Programming Specification (OPS) document.

1.1. Changes to the Protocol Defined Statistical Analysis Plan

Changes from the originally planned statistical analysis specified in the protocol are detailed in [Table 2](#)

Table 2 Changes to Protocol Defined Analysis Plan

Protocol Defined Analysis	SAP Defined Analysis	Rationale for Changes

 Population for analysis 	
 Enrolled population- All participants who passed screening and entered the study. Note screening failures (who never passed screening even if rescreened) and participants screened but never enrolled into the study (Reserve, Not Used) are excluded from the Enrolled analysis set as they did not enter the study. 	
 This population was not present in the protocol. It has been added to SAP as per the requirement for the data display

1.2. Objectives, Endpoints and Estimands

1.2.1. Objectives and Endpoints

Objectives	Endpoints ¹
Primary	

 To determine parent GSK3640254 and total drug-related radioactivity systemic concentrations following a single IV microtracer dose of [¹⁴C]-GSK3640254 (with an oral dose of non-radiolabelled 	
 AUC(0–inf), AUC(0–t), Cmax, tmax and t1/2 of parent and total drug-related material (radioactivity) in plasma and blood.

CONFIDENTIAL

Statistical Analysis Plan 213051

Objectives	Endpoints ¹
GSK3640254) and oral dose of [¹⁴ C]-GSK3640254 ¹	
 Volume of distribution at steady state (V_{ss}) and clearance (CL) of parent after IV dose (Period 1 only). Renal clearance of parent (CL_r) after both IV and oral dose Oral clearance (CL/F) and apparent volume of distribution (V_z/F) for the parent following oral administration

 To calculate the absolute oral bioavailability of GSK3640254 	
 Direct estimation of absolute oral bioavailability (F), indirect calculation of fraction of drug escaping first pass hepatic clearance (F_h), fraction absorbed (F_a) and fraction of drug escaping gut metabolism (F_g).

 To determine the rate and extent of excretion of total radioactivity in urine and feces and the total recovery of radioactivity, following IV and oral administrations of [¹⁴C]-GSK3640254 	
 Urinary and fecal cumulative excretion as a percentage of the total radioactive dose
Secondary	

 To evaluate the safety and tolerability of GSK3640254 after single IV and oral doses in healthy participants. 	
 Characterize observed adverse events, and abnormal laboratory, 12-lead ECG, and vital signs assessments observed.

 To determine the blood:plasma ratio of [¹⁴C]-GSK3640254-related materials (total radioactivity) associated with blood cellular components 	
 Blood:plasma ratio of [¹⁴C]-GSK3640254-related materials (total radioactivity).
Exploratory	

1.2.2. Estimands**Table 3 Estimands**

Objective	Estimand Category	Estimand			Population Level Summary Measure
		Variable/Endpoint	Analysis Set	Intercurrent Event Strategy	
Primary Objective: To determine parent GSK3640254 and total drug-related radioactivity systemic concentrations following a single IV microtracer dose of [¹⁴ C]-GSK3640254 (with an oral dose of non-radiolabelled GSK3640254) and oral dose of [¹⁴ C]-GSK36402541	Primary 1	AUC(0-inf), AUC(0-t), Cmax, tmax and t1/2 of parent and total drug-related material (radioactivity) in plasma	PK	Subject withdrawal or AE occurrence (treatment policy)	No adjustments will be made for the occurrence of any intercurrent events. Estimation will be done based upon observed data.
	Supplementary 1	Volume of distribution at steady-state (Vss) and clearance (CL) of parent after IV dose (Period 1 only)	PK	See Primary 1	
	Supplementary 2	Renal clearance of	PK	See Primary 1	

CONFIDENTIAL

Statistical Analysis Plan 213051

Objective	Estimand Category	Estimand			Population Level Summary Measure
		Variable/Endpoint	Analysis Set	Intercurrent Event Strategy	
		parent (CLr) after IV and oral administration			
	Supplementary 3	Oral clearance (CL/F) and apparent volume of distribution (Vz/F) for the parent following oral administration	PK	See Primary 1	
To calculate the absolute oral bioavailability of GSK3640254	primary 2	Direct estimation of absolute oral bioavailability (F), indirect calculation of fraction of drug escaping first pass hepatic clearance (Fh),	PK	See Primary 1	

CONFIDENTIAL

Statistical Analysis Plan 213051

Objective	Estimand Category	Estimand			Population Level Summary Measure
		Variable/Endpoint	Analysis Set	Intercurrent Event Strategy	
		fraction absorbed (Fa) and fraction of drug escaping gut metabolism (Fg).			
To determine the rate and extent of excretion of total radioactivity in urine and feces and the total recovery of radioactivity, following IV and oral administrations of [¹⁴ C]-GSK3640254	Primary 3	Urinary and fecal cumulative excretion as a percentage of the total radioactive dose		See Primary 1	
Key Secondary objective : To determine the blood:plasma ratio of [¹⁴ C]-GSK3640254-related materials (total radioactivity)	Secondary	Blood:plasma ratio of [¹⁴ C]-GSK3640254-related materials (total radioactivity).	PK	See Primary 1	

CONFIDENTIAL

Statistical Analysis Plan 213051

Objective	Estimand Category	Estimand			Population Level Summary Measure
		Variable/Endpoint	Analysis Set	Intercurrent Event Strategy	
associated with blood cellular components					

CONFIDENTIAL

Statistical Analysis Plan 213051

1.3. Study Design

Overview of Study Design and Key Features	

Screening: up to 30 days before first dose
 
Treatment Period 1 (Inpatient): [¹⁴C]GSK3640254 IV microtracer dose concomitant with oral tablet GSK3640254 dose. Sample collection for 7 days after dosing.
 
At least 13 days washout between doses.
 
Treatment Period 2 (Inpatient): Single oral dose of [¹⁴C]GSK3640254. Sample collection for 7 – 14 days after dosing*.
 
Follow up: 7 – 14 days after the last assessment.
 
*If radioactivity in the 24 hour interval collections immediately prior to discharge is still >1%, faecal samples will be collected by participants at home after Day 15 (day of discharge/follow up)
	
Design Features	
 • Open-label • Single center • Non-randomised • 2-period, single-sequence • Mass balance study • Approximately 6 healthy male participants will be enrolled • A screening visit (up to 30 days before first dose) • Two inpatient treatment periods (Treatment Periods 1 and 2), with at least 13 days between doses. 
A follow-up visit 7 – 14 days after the last assessment in Treatment Period 2

Study intervention	
Study intervention Assignment	
Approximately six participants will be enrolled to achieve at least 4 participants completing the two treatment periods. On Day 1 of Treatment Period 1, after an overnight fast of at least 8 h, each participant will take a single 200 mg oral dose (2 x 100 mg tablets) of GSK3640254 with a moderate fat meal (approximately 600 calories with approximately 30% of calories from fat); the IV infusion of 100 µg of [¹⁴C]-GSK3640254 (approximately 3.7 kBq; 100 nCi) will begin 5 h after oral dose and continue over 1 h. On Day 1 of Treatment Period 2, after an overnight fast of at least 8 h, each participant will receive approximately 85 mg [¹⁴C]-GSK3640254 (approximately 3.15 MBq; 85 µCi) as an oral suspension with a moderate fat meal (approximately 600 calories with approximately 30% of calories from fat).

Interim Analysis	There will be no formal interim analyses.

2. STATISTICAL HYPOTHESES / SUCCESS CRITERIA

This study is not designed for statistical testing and therefore has no formal statistical hypothesis.

Study objective will be evaluated descriptively and through estimation.

2.1. Multiple Comparisons and Multiplicity

No adjustments for multiple comparison will be made.

3. SAMPLE SIZE DETERMINATION

No formal sample size calculation has been performed for this study. However, the sample size reflects an accepted industry standard for human ADME studies using ¹⁴C radiolabelled drug. Additionally, the design of the study in terms of the concomitant administration of intravenous with oral administration (Period 1) inherently reduces variability in the parameters determined, versus a cross-over design for absolute bioavailability assessment, while enabling cross-over to Period 2 in the same participants. The primary objective of the study is to gain a better understanding of the compound's pharmacokinetic, excretory, and metabolic profile and 4 to 6 participants are deemed sufficient for this purpose. Six participants will be enrolled into the study. To minimize the number of participants exposed to radiation; those participants that discontinue early will not be replaced unless the total number of participants who complete both Periods 1 and 2 drops below 4.

4. ANALYSIS SETS

Analysis Set	Definition / Criteria	Analyses Evaluated
Screened	
 All participants who were screened for eligibility. This will be the population for reporting screened population data. 	
 Study Population
Enrolled	
 All participants who passed screening and entered the study. Note screening failures (who never passed screening even if rescreened) and participants screened but never enrolled into the study (Reserve, Not Used) are excluded from the Enrolled analysis set as they did not enter the study. 	
 Study Population
Safety	
 All participants who take at least 1 dose of study intervention. Participants will be analysed according to the treatment they received. This will be the population for reporting safety and study population data. 	
 Study / Safety Population
Pharmacokinetic (PK)	
 All participants in the Safety population who had at least 1 non-missing PK assessment (Non-quantifiable [NQ] values will be considered as non-missing values). 	
 PK Population

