7.2. Participant Discontinuation/Withdrawal from the Study

A participant may withdraw from the study at any time at his own request or may be withdrawn at any time at the discretion of the investigator for safety, behavioural, compliance or administrative reasons. If study intervention is permanently discontinued, the participant will remain in the study for confirmation of excretion of radioactivity (see Section [4.1.3](#)). Participants who withdraw from the study early should undergo an early withdrawal visit as defined in the SoA.

If the participant withdraws consent for disclosure of future information, the sponsor may retain and continue to use any data collected before such a withdrawal of consent.

If a participant withdraws from the study, he may request destruction of any samples taken and not tested, and the investigator must document this in the site study records.

The investigator will record in the source documents the results of follow-up examination of withdrawn participants, if the participant gives their consent.

In the event of vomiting directly after oral dosing withdrawal may be considered. Refer to Section [8.5.4](#) for details.

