8.5.4. Vomitus collection (if occurs)

Any episodes of vomiting should be recorded in the CRF as an adverse event.

If a participant vomits within the first 4 h after oral dosing, the participant will be considered unsuitable for evaluation and will be withdrawn from the study. Even if withdrawn, participants should remain in the clinic and samples collected until the discharge criteria outlined in Section [4.1.3](#) are met. Should the participant vomit after the first 4 h post oral dosing, the participant will not be withdrawn.

If a participant vomits any time during or after IV dosing, the participant will not be withdrawn.

As practical, the vomitus will be collected and the amount of radioactivity present in the vomitus estimated, using the sample handling procedure described for quantifying radioactivity in stools. During dosing, staff should ensure that each participant has a suitable pre-weighed plastic collection vessel available for that purpose.

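### The SAP keeps oral-dose PK data after vomiting within 4 h, although the protocol calls that participant not evaluable; Period 2 exposure, relative bioavailability and recovery are most exposed, F only slightly

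*SAP*

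**What the plan says.** Protocol 8.5.4 sets a window: "If a participant vomits within the first 4 h after oral dosing", then "the participant will be considered unsuitable for evaluation and will be withdrawn from the study". It goes on: "Even if withdrawn, participants should remain in the clinic and samples collected until the discharge criteria outlined in" Section 4.1.3 are met. It also says "Any episodes of vomiting should be recorded in the CRF as an adverse event", and asks for vomitus to be collected where practical and its radioactivity estimated. Protocol 7.2 is softer on the same event: "In the event of vomiting directly after oral dosing withdrawal may be considered".

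SAP 4 (like Protocol 9.3) defines the PK set as "All participants in the Safety population who had at least 1 non-missing PK assessment", with non-quantifiable values counted as non-missing. SAP 1.2.2, Table 3, names participant withdrawal and adverse events as intercurrent events under a treatment-policy strategy and states "No adjustments will be made for the occurrence of any intercurrent events". The other primary PK estimands and the blood:plasma ratio refer back to that entry. The exploratory suspension-versus-tablet comparison is not in Table 3; there SAP 5.4 applies the PK set alone.

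SAP 1.1, Table 2, declares one change from the protocol, the added Enrolled set. No rule for vomiting appears in SAP Tables 4 to 7.

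**The concern.** The protocol declares a participant not evaluable and the SAP evaluates him. He has at least one PK value, so he is in the PK set. His vomiting is an adverse event and his withdrawal is a withdrawal, so both fall under the strategy that changes nothing.

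The PK parameters are meant to describe the drug after an administered dose, not a dose partly lost. With four to six participants, a single low profile moves a geometric mean noticeably and widens the interval around a ratio. If the decision is left until the data are seen, in an open-label study of this size, any exclusion will look post hoc.

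**Working it through.** The plan has no sample-size or power figure to reproduce (SAP 3). The documents give no variability and no dose loss, so the values of L and CV below are assumptions.

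**1. A participant with both AUCs.** This is the Period 2 vomiter: his Period 1 data are intact and his suspension AUC is reduced. If a share L of exposure is lost, the mean log AUC (or log ratio) over n participants moves by ln(1−L)/n, so the geometric mean is multiplied by (1−L)^(1/n).

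| L | n=6 | n=4 |
|---|---|---|
| 50% | 0.5^(1/6) = 0.891 | 0.5^(1/4) = 0.841 |
| 70% | 0.3^(1/6) = 0.818 | 0.3^(1/4) = 0.740 |

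The same multipliers apply to Cmax if its loss is L. CL/F has AUC in the denominator, so its geometric mean rises: at 50% loss by 1/0.891 = 1.12 (n=6) or 1/0.841 = 1.19 (n=4). Vz/F rises equally if λz is unchanged.

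**2. Period 2 recovery.** SAP Table 5 sets Ae[total] to urine plus faeces and divides by the radiometric dose. If a share v of that dose leaves in vomitus, the mean total recovery falls by v/n. For v = 50% this is 50/6 = 8.3 percentage points (n=6) or 50/4 = 12.5 (n=4).

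**3. Absolute bioavailability if Protocol 8.5.4 is followed.** The infusion starts 5 h after the oral dose, after the 4 h window has closed. A Period 1 vomiter withdrawn under 8.5.4 has no IV AUC and no individual F. He enters the SAP Table 6 mixed model as one oral-only record beside five complete pairs. Its weight in the log oral/IV contrast is w = (1−ρ)/6, where ρ = s_b²/(s_b²+s_w²) and s² = ln(1+CV²).

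- Between-subject CV 30%, within-subject CV 10%: s_b² = 0.0862, s_w² = 0.00995, ρ = 0.896, w = 0.017. At 50% loss the multiplier is 0.5^0.017 = 0.988.
- Both CVs 30%: ρ = 0.5, w = 0.083. At 50% loss the multiplier is 0.5^0.083 = 0.944.

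So oral/IV shifts by about 1–6% at 50% loss. Table 6 reports IV/oral, so its printed ratio would rise, by 1/0.988 = 1.01 to 1/0.944 = 1.06. The model uses Period 1 only, so a Period 2 vomiter cannot enter it.

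**4. When F takes the full shift of step 1.** Two routes are left open. The IV dose may still be given, since Protocol 7.2 makes withdrawal optional. Or the per-subject F in SAP Table 4 may use the Period 2 oral AUC: Table 4 defines the oral dose as radiometric, and only the Period 2 oral dose is labelled.

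**5. Effect on the interval.** In a simulation of paired 90% intervals (20,000 runs, n=6, true ratio 1, one vomiter at 50% loss), the results were as follows.

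| Within-subject CV | Quantity | No vomiter | Kept | Excluded (n=5) |
|---|---|---|---|---|
| 20% | Upper/lower limit ratio | 1.55 | 1.88 | 1.65 |
| 10% | Chance that the interval lies in 0.80–1.25 | 0.90 | 0.02 | 0.79 |

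A true ratio of 1 presumes dose-normalised parameters, which SAP Table 7 does not state. The multipliers in step 1 do not depend on this.

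**6. How often.** With an assumed early-vomiting rate of 2, 5 or 10% per participant, the chance of at least one among six is 1−0.98^6 = 11%, 1−0.95^6 = 26% or 1−0.90^6 = 47%.

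**The case against.** A reader might infer from step 1 that F itself is biased downwards by 11% or more. The documents do not support that as the general case. Under Protocol 8.5.4 the design largely protects F (step 3), and the larger figure needs one of the two routes in step 4. Nor does the SAP say that oral AUC is divided by the nominal dose: Table 4 uses a radiometric dose, Table 6 the corresponding dose, and Table 7 states no division.

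Membership of the PK set does not force every parameter into every summary. SAP 5.2.1.2.1 derives parameters only where the data allow, and Tables 6 and 7 run only with adequate profiles. Neither filter is defined or tied to vomiting, and a participant who loses half the dose can still give a complete, low profile. The SAP's one restriction to participants who completed both periods belongs to the Table 7 fallback for non-convergence.

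Data handling is deferred to the Output and Programming Specification, which is not available and may hold an exclusion rule. That limits confidence, but such a rule would contradict Table 3 as written.

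Continued sampling is clear only for Period 2, because Protocol 4.1.3 concerns recovery in that period. For a Period 1 vomiter its extent is undefined, though any sample already taken puts him in the PK set.

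The study is descriptive, such a profile would be visible in the listings, and the human GI events listed in Protocol 2.3.1 for the multiple-dose part of Study 207187 do not include vomiting (dogs did vomit). All of this lowers the likelihood and the stakes. GI intolerability is still a named risk, and visibility in a listing does not settle what enters the summary.

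**Conclusion.** The plan is wrong as written on this point. It retains, without adjustment, oral-dose data that the protocol calls not evaluable. If the event occurs, the main effects are on Period 2 suspension AUC and Cmax, CL/F, Vz/F, the exploratory suspension/tablet ratio and urine-plus-faeces recovery. One participant with both AUCs and an assumed 50–70% loss lowers the geometric mean oral AUC or ratio by 11–18% with six participants and 16–26% with four. For F the effect is about 1–6% at 50% loss under Protocol 8.5.4 and the assumed CVs; the full shift arises only through the open wording noted above. Confidence is moderate, because the bias depends on an event and one governing document is unavailable.

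**What to change.** In SAP 4, with matching text in Tables 6 and 7, state that PK parameters from an oral dose followed by vomiting within the protocol's window are listed but excluded from the summaries and from both models. Data from an unaffected period stay in, and a sensitivity run includes the excluded values. Replace the treatment-policy entry for this event in Table 3 so that it agrees.

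For Period 2 recovery, state how vomitus radioactivity is counted, or report that participant's recovery separately with a flag. State which period's oral dose and AUC enter the Table 4 formula for F.

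Protocol 7.2 and 8.5.4 must be reconciled on withdrawal after vomiting; which rule applies is for the sponsor to decide.

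The cost is SAP and protocol wording. The downside is one fewer evaluable profile if the event occurs: at n=6 and 20% within-subject CV the average interval is then wider than with six clean profiles (1.65 against 1.55) but narrower than with the vomiter kept (1.88).
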